6.4. Study Intervention Compliance

All doses of investigational product will be administered by the appropriately designated study staff at the investigator site.

6.5. Concomitant Therapy

6.5.1. Prohibited Concomitant Vaccines and Treatments

- Receipt of any investigational vaccines, drugs, or medical devices is prohibited during participant participation in the study.
- Receipt of any nonstudy pneumococcal vaccine is prohibited during participant participation in the study.

6.5.2. Permitted Concomitant Vaccines and Treatments

- Other routine pediatric vaccines, including influenza vaccine, are permitted at any time throughout study participation, given according to official local recommendations/regulations.
- The use of prophylactic antipyretic/pain medication, while permitted, is not recommended on the day of investigational product administration (before or after vaccination).
- Inhaled/nebulized, topical (skin, eyes, or ears), or localized injections of corticosteroids (eg, intra-articular or intrabursal administration) are permitted during participant participation in the study.
- Prescription and nonprescription medications, vitamins, minerals, and herbal remedies are permitted during participant participation in the study.

6.5.3. Recording Prior and Concomitant Vaccines and Treatments

The name, date of administration, and site of administration for all vaccinations given on the same day as investigational product administration (Visits 1, 2, 3 and 5) will be recorded in the CRF. At Visit 1, information on prior vaccinations received by the participant will be recorded in the CRF.

Concomitant medications used to treat an NDCMC or SAE should be collected from the signing of informed consent through 6 months after Dose 4 (Visit 7 telephone call) and will be recorded in the CRF.

6.6. Dose Modification

Not applicable.

6.7. Intervention After the End of the Study

No intervention will be provided to study participants at the end of the study.

7. DISCONTINUATION OF STUDY INTERVENTION AND PARTICIPANT DISCONTINUATION/WITHDRAWAL

7.1. Discontinuation of Study Intervention

Participant eligibility must be confirmed prior to each vaccination in order to continue in the study.

If a participant no longer meets the eligibility criteria during the vaccination period of the study, further vaccinations should be discontinued, but the participant may remain in the study. If a participant is discontinued from vaccination and the participant's parent(s)/legal guardian(s) consents, safety follow-up will be conducted as per Section 7.2.

See the SoA for data to be collected at the time of intervention discontinuation and follow-up and for any further evaluations that need to be completed.

7.2. Participant Discontinuation/Withdrawal From the Study

A participant may be withdrawn from the study at any time at the request of his/her parent(s)/legal guardian(s) or may be withdrawn at any time at the discretion of the investigator for safety, behavioral, compliance, or administrative reasons.

If a participant does not return for a scheduled visit, every effort should be made to contact the participant's parent(s)/legal guardian(s). All attempts to contact the participant's parent(s)/legal guardian(s) and information received during contact attempts must be documented in the participant's source document. In any circumstance, every effort should be made to document participant outcome, if possible.

At the time of discontinuing please refer to the study reference manual (SRM) and SoA for assessments to be collected at the time of study discontinuation and follow-up and for any further evaluations that need to be completed.

The participant's parent(s)/legal guardian(s) should ideally notify the investigator in writing of the decision to withdraw consent from future follow-up, whenever possible. The participant's parent(s)/legal guardian(s) should be questioned regarding their reason for withdrawal. The participant will be permanently discontinued both from the study intervention and from the study at that time. The investigator or his or her designee should capture the reason for withdrawal in the CRF for all participants.

The participant should be requested to return for a final visit, if applicable, and the investigator will perform the procedures indicated for the next visit. Any AEs or SAEs that are continuing at the time of withdrawal from the study should be followed until resolution or in case of permanent impairment, until the condition stabilizes.

For participants who are discontinued prior to completing all 4 doses of study intervention, the parent(s)/legal guardian(s) should be encouraged to follow up with their primary care physician to have the participant complete the pneumococcal conjugate vaccine series as part of their recommended standard of care.

A final telephone contact 6 months after the last vaccination (similar to Section 8.10.7) for the collection of safety information should be completed for all participants who have been withdrawn after administration of investigational product, unless consent for further contact has been withdrawn, or the participant is lost to follow-up. Participant withdrawal should be explained in the source documents and should include whether the withdrawal is only from further receipt of investigational product or also from study procedures and/or postvaccination study follow-up.

If a participant is withdrawn from the study, his/her parent(s)/legal guardian(s) may request destruction of any remaining samples, but data already generated from the samples will continue to be available, and may be used to protect the integrity of existing analyses. The investigator must document any such requests in the site study records.

If the participant is withdrawn from the study and his/her parent(s)/legal guardian(s) also withdraws consent (see below) for disclosure of future information, no further evaluations should be performed and no additional data should be collected. The sponsor may retain and continue to use any data collected before such withdrawal of consent.

When a participant is withdrawn from the study because of an SAE, the SAE must be recorded on the CRF and reported on the VaccineCT SAE Reporting Form.

Lack of completion of all or any of the withdrawal/early termination procedures will not be viewed as protocol deviations so long as the participant's safety was preserved.

7.3. Lost to Follow-up

A participant will be considered lost to follow-up if he or she repeatedly fails to return for scheduled visits and the participant's parent(s)/legal guardian(s) is unable to be contacted by the study site.

The following actions must be taken if a participant fails to return to the clinic for a required study visit or fails to respond to the 6-month safety follow-up telephone call:

- The site must attempt to contact the participant's parent(s)/legal guardian(s) and reschedule the missed visit as soon as possible and counsel the participant's parent(s)/legal guardian(s) on the importance of maintaining the assigned visit schedule and ascertain whether or not the participant's parent(s)/legal guardian(s) wishes the participant to, and/or should, continue in the study;
- Before a participant is deemed lost to follow-up, the investigator or designee must make every effort to regain contact with the participant's parent(s)/legal guardian(s) (where possible, 3 telephone calls and, if necessary, a certified letter to the participant's last known mailing address or local equivalent methods). These contact attempts should be documented in the participant's medical record;
- Should the participant's parent(s)/legal guardian(s) continue to be unreachable, the participant will be considered to have been withdrawn from the study.

Discontinuation of specific sites or of the study as a whole is handled as part of Appendix 1.

8. STUDY ASSESSMENTS AND PROCEDURES

The investigator (or an appropriate delegate at the investigator site) must obtain a signed and dated ICD before performing any study-specific procedures.

Study procedures and their timing are summarized in the SoA. Protocol waivers or exemptions are not allowed.

Immediate safety concerns should be discussed with the sponsor immediately upon occurrence or awareness to determine if the participant should continue or discontinue study intervention.

Adherence to the study design requirements, including those specified in the SoA, is essential and required for study conduct.

All screening evaluations must be completed and reviewed to confirm that potential participants meet all eligibility criteria. The investigator will maintain a screening log to record details of all participants screened and to confirm eligibility or record reasons for screening failure, as applicable.

Every effort should be made to ensure that protocol-required tests and procedures are completed as described. However, it is anticipated that from time to time there may be circumstances outside the control of the investigator that may make it unfeasible to perform the test. In these cases, the investigator must take all steps necessary to ensure the safety and well-being of the participant.

When a protocol-required test cannot be performed, the investigator will document the reason for the missed test and any corrective and preventive actions that he or she has taken to ensure that required processes are adhered to as soon as possible. The study team must be informed of these incidents in a timely manner.

For samples being collected and shipped, detailed collection, processing, storage, and shipment instructions and contact information will be provided to the investigator site prior to initiation of the study.

8.1. Efficacy Assessments

Not applicable.

8.2. Safety Assessments

A clinical assessment, including medical history and measurement of temperature as appropriate for the age of the child, according to routine local practice, will be performed on all participants prior to vaccination to determine participant eligibility and to establish a clinical baseline. Significant medical history and significant findings observed during physical examination (if performed) will be recorded in the medical history CRF. Temperature measurement prior to vaccination will be documented and recorded in the CRF.

The participant will be observed for 30 minutes after each vaccination and any reactions during the visit will be assessed and recorded.

Prompted e-diary events, including local reactions (redness, swelling, and pain at the injection site) and systemic events (fever, decreased appetite, drowsiness/increased sleep, and irritability) that occur within 7 days following investigational product administration (Days 1 to 7, where Day 1 is the day of vaccination) are graded as described in Section 8.2.2. Furthermore, AEs, SAEs, and NDCMCs will be collected as defined in Section 10.3.

Planned time points for all safety assessments are provided in the SoA. Unscheduled clinical laboratory measurements may be obtained at any time during the study to assess any perceived safety concerns.

8.2.1. Participant Electronic Diary

The participant's parent(s)/legal guardian(s) will be asked to monitor and record local reactions, specific systemic events, and antipyretic/pain medications taken for 7 days, each evening following each vaccination using an e-diary (in a provisioned device or application on a personal device), which allows recording of these assessments only within a fixed time window, thus providing the accurate representation of the participant's experience. Data on local reactions, specific systemic events, and antipyretic/pain medications reported in the e-diary will be transferred electronically to the e-diary vendor, where they will be available for review by investigators, their qualified designees, and sponsor staff at all times via an internet-based portal. At intervals agreed to by the vendor and Pfizer, these data will be transferred electronically to Pfizer for analysis and reporting.

The daily e-diary data will not be captured in the CRF. However, if a participant is withdrawn because of prompted events reported in the e-diary, the event(s) should be recorded on the AE page of the CRF, regardless of whether the investigator considers the event(s) to be clinically significant.

The investigator or designee must obtain stop dates for any local reactions and specific systemic events ongoing on the last day that the e-diary was completed. The stop dates should be entered in the CRF.

Investigators (or an appropriately qualified designee) are required to review the e-diary data online at frequent intervals (daily is optimal) to evaluate participant compliance and reported events as part of the ongoing safety review.

8.2.2. Grading Scale for Prompted Events

The grading scales used in this study to assess prompted events as described below are based on concepts outlined in the FDA Center for Biologics Evaluation and Research (CBER) guidelines on toxicity grading scales for adults and adolescent volunteers enrolled in preventive vaccine clinical trials, but have been adapted for applicability to healthy infants.⁷³

8.2.2.1. Local Reactions

For the first 7 days following each vaccination from Day 1 through Day 7, the participant's parent(s)/legal guardian(s) will be asked to assess redness, swelling, and pain at the 20vPnC or 13vPnC injection site and to record the symptoms in the e-diary in the evening. Redness and swelling will be measured and recorded in measuring device (caliper) units (range: 1 to >14; an entry in the e-diary of 15 will denote >14), and then categorized during analysis as mild, moderate, or severe based on the grading scale in Table 1 below. Measuring device units can be converted to centimeters according to the following scale: 1 measuring device unit = 0.5 cm. Pain at the vaccine injection site will be assessed by the participant's parent(s)/legal guardian(s) as mild, moderate, or severe according to the grading scale in Table 1 below. The participant's parent(s)/legal guardian(s) will be prompted to contact the investigator if the participant experiences a severe (Grade 3) or above local reaction to assess the reaction and perform an unscheduled assessment or visit as appropriate.

Only an investigator is able to classify a participant's local reaction as Grade 4, after physical examination of the participant or documentation from another medically qualified source (eg, emergency room or hospital record). If a participant experiences a Grade 4 local reaction, the investigator must immediately notify the sponsor. Site staff will educate the participant's parent(s)/legal guardian(s) regarding signs and symptoms that would prompt site contact.

The procedure for notification of the sponsor is provided in the investigator site file (ISF) or equivalent.

	GRADE 1 Mild	GRADE 2 Moderate	GRADE 3ª Severe	GRADE 4 ^b
Redness	1 to 4 caliper units (or measuring device units) = >0 to 2.0 cm	5 to 14 caliper units (or measuring device units) = >2.0 to 7.0 cm	>14 caliper units (or measuring device units) = >7 cm	Necrosis or exfoliative dermatitis
Swelling	1 to 4 caliper units (or measuring device units) = >0 to 2.0 cm	5 to 14 caliper units (or measuring device units) = >2.0 to 7.0 cm	>14 caliper units (or measuring device units) = >7 cm	Necrosis
Pain at injection site (tenderness)	Hurts if gently touched (eg, whimpers, winces, protests, or withdraws)	Hurts if gently touched, with crying	Causes limitation of limb movement	Emergency room visit or hospitalization for severe pain (tenderness) at injection site

Table 1. Grading Scales for Local Reactions

Abbreviations: CRF = case report form; e-diary = electronic diary.

Note: If the size of the redness and/or swelling falls between 2 measuring device units, the higher measuring device unit number will be recorded in the e-diary.

- a. Parents/legal guardians of the participants experiencing local reactions >14 caliper units (>7.0 cm) are to be contacted by the study site. An unscheduled visit may be required.
- b. Grade 4 assessment should be made by the investigator. Grade 4 will not be collected in the e-diary but will be collected as an AE in the CRF. The severity of the local reaction should be graded using the AE severity grading scale provided in the protocol.

8.2.2.2. Systemic Events – Symptoms and Fever

8.2.2.2.1. Symptoms

For the first 7 days following each vaccination from Day 1 through Day 7, the participant's parent(s)/legal guardian(s) will be asked to assess decreased appetite, drowsiness/increased sleep, and irritability and to record the symptoms in the e-diary (in a provisioned device or application on a personal device) in the evening. The symptoms will be assessed by the participant's parent(s)/legal guardian(s) as mild, moderate, or severe according to the grading scale in Table 2 below.

The participant's parent(s)/legal guardian(s) will also be instructed to contact site staff if the participant experiences any possible Grade 4 prompted systemic event (ie, emergency room visit or hospitalization for severe decreased appetite, severe drowsiness/increased sleep, or severe irritability) within 7 days after vaccination. Study staff may also contact the participant's parent(s)/legal guardian(s) to obtain additional information on Grade 3 events entered into the e-diary.

Only an investigator is able to classify a participant's systemic event as Grade 4, after physical examination of the participant or documentation from another medically qualified source (eg, emergency room or hospital record) or telephone contact with the participant's parent(s)/legal guardian(s). If a participant experiences a Grade 4 systemic event, the investigator must immediately notify the sponsor.

The procedure for notification of the sponsor is provided in the ISF or equivalent.
Systemic Event	GRADE 1 Mild	GRADE 2 Moderate	GRADE 3 Severe	GRADE 4 ^a
Decreased appetite (loss of appetite)	Decreased interest in eating	Decreased oral intake	Refusal to feed	Emergency room visit or hospitalization for severe decreased appetite (loss of appetite)
Drowsiness (increased sleep)	Increased or prolonged sleeping bouts	Slightly subdued, interfering with daily activity	Disabling, not interested in usual daily activity	Emergency room visit or hospitalization for severe drowsiness (increased sleep)
Irritability (fussiness) (synonymous with restless sleep; decreased sleep)	Easily consolable	Requiring increased attention	Inconsolable; crying cannot be comforted	Emergency room visit or hospitalization for severe irritability (fussiness)

 Table 2.
 Grading Scales for Systemic Events

Abbreviations: CRF = case report form; e-diary = electronic diary.

a. Grade 4 assessment should be made by the investigator. Grade 4 will not be collected in the e-diary but will be collected as an AE in the CRF. The severity of the systemic event should be graded using the AE severity grading scale provided in the protocol.

8.2.2.2.2. Fever

In order to record information on fever, a digital thermometer will be given to the participant's parent(s)/legal guardian(s) with instructions on how to measure temperature (as appropriate for the age of the child) at home. Temperature will be collected in the evening, daily, for 7 days following vaccination (Days 1 to 7, where Day 1 is the day of vaccination) and at any time during the 7 days that fever is suspected. Fever is defined as a temperature of \geq 38.0°C (\geq 100.4°F). The highest temperature for each day will be recorded in the e-diary. In the event of a fever on Day 7, temperature will be collected daily until fever has resolved (1 day of temperature less than 38.0°C [100.4°F]) in order to collect a stop date in the CRF. A participant's parent(s)/legal guardian(s) will be prompted to contact the investigator if the participant experiences a temperature \geq 40.0°C (\geq 104.0°F) to assess the fever and perform an unscheduled assessment, as applicable (see unscheduled assessments in Section 8.10.8). Study staff may also contact the participant's parent(s)/legal guardian(s) to obtain additional information if a temperature of \geq 38.9°C (\geq 102.0°F) is entered into an e-diary. Temperature will be measured and recorded to 1 decimal place and then grouped into ranges for the analysis; see Table 3 below.

Table 3.Ranges for Fever

≥38.0°C to 38.4°C		
>38.4°C to 38.9°C		
>38.9°C to 40.0°C		
>40.0°C		

Note: Fever is defined as temperature $\geq 38.0^{\circ}$ C.

8.2.2.3. Use of Antipyretic/Pain Medication

The participant's parent(s)/legal guardian(s) will be asked to record the use of antipyretic/pain medication (yes/no) in the e-diary (in a provisioned device or application on a personal device) in the evening, daily, for 7 days after each dose of investigational product, where Day 1 is the day of vaccination.

The use of prophylactic antipyretic/pain medication, while permitted, is not recommended on the day of investigational product administration (before or after vaccination).

8.2.3. Clinical Safety Laboratory Assessments

Clinical safety laboratory assessments are not required by this protocol.

If laboratory values from non–protocol-specified laboratory assessments performed at the institution's local laboratory require a change in participant management or are considered clinically significant by the investigator (eg, SAE or AE or dose modification), then the results must be recorded in the CRF.

8.2.4. Biological Samples

Collection of biological samples are not required by this protocol.

8.3. Adverse Events and Serious Adverse Events

The definitions of an AE and an SAE can be found in Appendix 3.

AEs will be reported by the participant's parent(s)/legal guardian(s). Events that, in the clinical judgment of the investigator, are 1) consistent with normal growth and development and 2) do not differ significantly in frequency or severity from expected are not generally to be considered AEs. Examples may include, but are not limited to, teething, contact diaper rash, spitting up, colic, or typical fussiness/crying in infants and children.

The investigator and any qualified designees are responsible for detecting, documenting, and recording events that meet the definition of an AE or SAE and remain responsible to pursue and obtain adequate information both to determine the outcome and to assess whether it meets the criteria for classification as an SAE or that caused the participant to discontinue from the study (see Section 7).

In addition, the investigator may be requested by Pfizer Safety to obtain specific follow-up information in an expedited fashion.

8.3.1. Time Period and Frequency for Collecting AE and SAE Information

The time period for actively eliciting and collecting AEs and SAEs ("active collection period") for each participant begins from the time the participant's parent(s)/legal guardian(s) provides informed consent, which is obtained before the participant's participation in the study (ie, before undergoing any study-related procedure and/or receiving investigational product), through and including Visit 4, and from Visit 5 to Visit 6. Between Visit 4 and Visit 5, only SAEs and NDCMCs will be reported. At Visit 7 (final telephone contact), the participant's parent(s)/legal guardian(s) will be contacted by telephone to inquire about SAEs, including hospitalizations and NDCMCs, since Visit 6.

AEs that begin before the start of study intervention but after obtaining informed consent will be recorded on the Medical History/Current Medical Conditions section of the CRF, not the AE section.

Follow-up by the investigator continues throughout and after the active collection period and until the event or its sequelae resolve or stabilize at a level acceptable to the investigator, and Pfizer concurs with that assessment.

Investigators are not obligated to actively seek AEs or SAEs after conclusion of the study participation. However, if the investigator learns of any SAE, including a death, at any time after a participant has completed or withdrawn early from the study, and he/she considers the event to be reasonably related to the study intervention or study participation, the investigator must promptly notify the sponsor.

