8.3.1.1. Reporting SAEs to Pfizer Safety

All SAEs occurring in a participant during the active collection period are reported to Pfizer Safety on the Vaccine SAE Reporting Form immediately upon awareness and under no circumstance should this exceed 24 hours, as indicated in Appendix 3. The investigator will submit any updated SAE data to the sponsor within 24 hours of it being available.

SAEs occurring in a participant after the active collection period has ended are reported to Pfizer Safety if the investigator becomes aware of them; at a minimum, all SAEs that the investigator believes have at least a reasonable possibility of being related to investigational product must be reported to Pfizer Safety.

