8.3.1.2. Recording Nonserious AEs and SAEs on the CRF

During the active collection period, both nonserious AEs and SAEs are recorded on the CRF.

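### The protocol's active collection period for SAEs stops at Visit 6 although SAEs are elicited to Visit 7, so later SAEs fall under a reporting rule with no deadline and a weaker minimum than Section 10.3.4

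*Protocol*

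**What the plan says.** Protocol Section 8.3.1 introduces the term active collection period for the eliciting of AEs and SAEs alike. It starts at informed consent and runs "through and including Visit 4, and from Visit 5 to Visit 6". The section then adds two statements about SAEs outside that period:

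- For the gap before the fourth dose: "Between Visit 4 and Visit 5, only SAEs and NDCMCs will be reported".
- For the final call at Visit 7, parents "will be contacted by telephone to inquire about SAEs, including hospitalizations and NDCMCs, since Visit 6".

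Its last paragraph deals with SAEs learned of "at any time after a participant has completed or withdrawn early from the study". There the investigator must notify the sponsor of those considered reasonably related to the study intervention or to participation.

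Two operative rules use the defined term.

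- **Section 8.3.1.1, within the period:** "All SAEs occurring in a participant during the active collection period are reported to Pfizer Safety", immediately and never later than 24 hours, with a reference to Appendix 3.
- **Section 8.3.1.1, after the period:** "SAEs occurring in a participant after the active collection period has ended are reported to Pfizer Safety if the investigator becomes aware of them". The stated minimum is that "all SAEs that the investigator believes have at least a reasonable possibility of being related to investigational product must be reported". No time limit is given for the initial report.
- **Section 8.3.1.2:** "During the active collection period, both nonserious AEs and SAEs are recorded on the CRF".

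Elsewhere SAE collection is longer. The synopsis (1.1), the SAE and NDCMC row of the Schedule of Activities (1.3) and Section 8.10.7 run it to Visit 7. SAP Section 3.1.1 sets the primary SAE endpoint from Dose 1 through 6 months after Dose 4, and SAP Section 3.1.1.5 collects SAEs to the end of the study. The Section 10.3.4 table requires all SAEs on the CRF and all on the reporting form within 24 hours of awareness.

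**The concern.** A period ending at Visit 6 suits nonserious AEs, whose collection does stop there. It does not suit SAEs, which the protocol goes on actively eliciting until Visit 7. Because the 24-hour duty and the CRF rule both depend on the term, an SAE between Visits 6 and 7 falls, read literally, under the paragraph for events after collection has ended.

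Sites can learn of such events well before the Visit 7 call: at Visit 6 (Section 8.10.6) parents are told to contact the site at once about an emergency room visit or hospitalization. A site working from Section 8.3.1.1 alone could report such an event later than 24 hours. It could also fall back on the stated minimum and leave out one that it judges unrelated.

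Withdrawn participants raise a similar problem. Section 7.2 and footnote h of the Schedule of Activities plan a 6-month call that collects any SAE, while the Section 8.3.1 sentence that names early withdrawal requires notification only of related ones.

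What is at stake is the timeliness and completeness of expedited reporting in a study whose only primary objective is safety. Section 8.3.4 itself calls prompt notification essential.

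**Working it through.** The plan gives no figure to reproduce on this point. The check is a comparison of rules, followed by date arithmetic on the visit windows.

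**Rules for an SAE that occurs between Visits 6 and 7**

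| Source | Reported to sponsor safety | Deadline | Recorded on CRF |
|---|---|---|---|
| 8.3.1.1, within the active collection period (for comparison) | All | 24 hours | Yes (8.3.1.2) |
| 8.3.1.1, after that period | Reported on awareness; mandatory minimum is possibly related SAEs | None stated | 8.3.1.2 is silent |
| 8.10.7 (Visit 7) | Points to Section 10.3 | Points to Section 10.3 | CRF completed |
| 10.3.4 table, SAE row | All | 24 hours from awareness | All |

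Section 10.3.5 also assumes 24 hours. Section 8.3.1.1 cites Appendix 3 only in its within-period sentence, so that citation does not carry the deadline over to later events.

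**Length of the affected stretch, original windows**

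Inputs: Visit 6 is 28 to 42 days after Visit 5, and Visit 7 is 168 to 196 days after Visit 5 (Sections 1.3 and 4.1).

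- Shortest: 168 − 42 = 126 days.
- Longest: 196 − 28 = 168 days.
- Window midpoints: 182 − 35 = 147 days.

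**Amendment 1 windows**

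Inputs: the Visit 7 windows in Section 10.9, all closing by 31 Aug 2022. The cap below is the number of days from Visit 5 to that date.

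| Visit 5 (Dose 4) date in 2022 | Visit 7 window (days after Visit 5) | Cap, first to last date | Shortest Visit 6 to 7 | Longest Visit 6 to 7 |
|---|---|---|---|---|
| 17 Feb to 14 Mar | 168 to 196 | 195 to 170 | 168 − 42 = 126 | 195 − 28 = 167 |
| 15 Mar to 1 Apr | 145 to 168 | 169 to 152 | 145 − 42 = 103 | 168 − 28 = 140 |
| 2 Apr to 20 Apr | 126 to 145 | 151 to 133 | 126 − 42 = 84 | 145 − 28 = 117 |

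The minimum over all windows is 84 days.

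**Share of the SAE endpoint period, original windows**

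This takes Dose 1 at 42 to 98 days of age and Visit 5 at 365 to 455 days of age. The time from Dose 1 to Visit 7 is age at Visit 5, plus the Visit 7 offset, minus age at Dose 1.

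- Smallest share: 126 / (455 + 168 − 42) = 126 / 581 = 22%.
- Largest share: 168 / (365 + 196 − 98) = 168 / 463 = 36%.

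The Visit 4 to Visit 5 interval also lies outside the literal period. It is not counted here, because Section 8.3.1 says that SAEs are reported in it; the text there is only ambiguous.

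**The case against.** The strongest reply is that the protocol already contains the right rule. The 10.3.4 table has no limit by visit or relatedness, Visit 7 sends sites to Section 10.3, and the Schedule of Activities row for recording and reporting SAEs runs to Visit 7. Section 8.3.1.1 is silent on a later deadline and does not permit a longer one, so a site can obey both. Its first clause says that later SAEs are reported on awareness, and the related-only wording is just a floor. Section 8.3.1.2 does not forbid CRF entry after the period. The related-only sentence for withdrawn participants follows a statement about not seeking events after participation ends, so it may be meant for unsolicited information. The day counts measure visit spacing, not harm.

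Much of this stands. Following Section 10.3 breaches nothing, and no loss of endpoint data is shown. The scope for omission is narrow, since Section 10.3.4 has events of unknown causality handled as related. What remains is that the protocol gives two different statements of the duty for the same event and does not say which prevails. A floor limited to related SAEs is not the same as all SAEs, and the missing deadline is not supplied where the reporting rule is set out. The sentence on early withdrawal does, as written, cover participants who are still due a planned safety call.

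**Conclusion.** The concern holds. The active collection period as defined does not match the protocol's own SAE collection, and the reporting rule tied to it is inconsistent with Section 10.3.4 for SAEs after Visit 6. The stretch is 126 to 168 days under the original windows and no shorter than 84 days for any participant seen within the windows.

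These are lengths of time, not counts of late or missed reports. The documents give no SAE rate, so none can be derived. The practical effect rests on a site reading Section 8.3.1.1 literally and not turning to Section 10.3. The point bears on expedited reporting; it gives no ground for doubting the primary SAE percentage. It should be corrected, because it concerns a safety-reporting duty and the correction is cheap.

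**What to change.** Reconcile the passages as follows.

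1. In Section 8.3.1, keep the present period for nonserious AEs. Define a separate SAE and NDCMC period from informed consent through Visit 7, or through the 6-month contact for withdrawn participants.
2. In Sections 8.3.1.1 and 8.3.1.2, make the 24-hour rule and the CRF rule refer to that period for SAEs.
3. Limit the Section 8.3.1.1 paragraph on later SAEs, and the related-only sentence in Section 8.3.1, to events after that period.

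The cost is wording only, with no new visits or data. A protocol amendment needs IRB/EC approval (Section 10.1.1). A clarification to sites that Section 10.3.4 governs SAEs through Visit 7 is quicker, and timing favors it. Amendment 1 closes Visit 7 by 31 Aug 2022 for participants dosed after 16 Feb 2022, and for a Dose 4 on 16 Feb 2022 the original 196-day limit falls on the same date.
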